7.0 Setting

The research will be done at the MUSC/VA Rehabilitation Research space located at [name]. The following labs will be utilized:

Locomotor Energetics and Assessment Laboratory (LEA): The LEA is a 988 square foot laboratory located in the College of Health Professions Research Building on the campus of Medical University of South Carolina. The laboratory is a shared resource of the college and is supported in part by the Department of Health Sciences and Research. The laboratory is located in the same building as the offices of the PI, Co-I and staff. It features equipment capable of collecting kinematic, kinetic, electromyographic, strength, and metabolic data. A substantial investment in improving the capabilities of the laboratory will be funded by the startup funds of the PI. The motion analysis laboratory is adjacent to a small workshop available for the construction, repair, and alteration of simple mechanical devices.

The Locomotor Rehabilitation Laboratory (LRL): is a state-of-the-art treatment laboratory, designed to offer a full range of locomotor interventions for those with impaired walking secondary to neurologic injury. The LRL is an 808 square foot laboratory located on the second floor of the College of Health Professions Research Building, Room C-213. The laboratory houses a ZeroG mobile body weight support system (only the 6th one installed nationally) designed to create a permissive environment for retraining walking ability not only over a treadmill, but also over level ground and environmental obstacles.

Research participants will have access to a Woodway split-belt treadmill, for training cardiovascular endurance as well as lower extremity strength and power. Additional assessment capabilities include: 8 camera Phase Space Motion Capture system, Delsys Wireless EMG system, and Biomed Dynamometer. The research will focus on a multi-faceted approach to locomotor recovery after neurological injury, initially targeting stroke and spinal cord injury. The overall goal is to understand and improve clinical decision making relative to locomotor interventions.

Motor Performance Laboratory (MPL): The MPL is an approximately 914 ft² room located in the College of Health Professions Research Building, Room C102. The primary focus of the MPL is to investigate the neural and muscular mechanisms underlying muscle function in people with neurological conditions, such as post-neurological injury i.e. stroke or spinal cord injury and/or healthy controls. An additional focus is the development of effective interventions to counteract these neuromuscular impairments and improve overall function, activity, and participation. Research participants will have access to a Woodway treadmill, a Precor elliptical trainer, Shuttle Systems jump trainers (MVP and 2000), recumbent and upright bikes, NUSTEP Recumbent Stepper, Full metabolic and EKG cart, and passive safety rail and harness system all aimed at improving and measuring lower extremity function and physical function.

The Functional Neuro-Stimulation Laboratory (FNSL): The FNSL is located on the 2nd floor of the College of Health Professions Research Building on the campus of Medical University of South Carolina. FNSL studies use electromagnetic approaches as either research tools investigating neuroscience questions or as investigational or FDA approved treatments for brain diseases. Techniques actively being used by FNSL researchers and their collaborators include transcranial magnetic stimulation (TMS) and transcranial direct current stimulation (tDCS)

8.0 Recruitment Methods

Subject Recruitment: Participants for this program will be recruited from the Ralph H. Johnson VA Health Care System and the Medical University of South Carolina (MUSC). The Ralph H. Johnson VAHCS and MUSC share core facilities through a memorandum of understanding which provide a unique environment from which to recruit participants. The combination of the Ralph H. Johnson VAHCS and the MUSC Stroke Program sees over 60 new stroke patients per month and all patients are routinely screened for eligibility to our various research studies. Potential participants will be given information while inpatient and again when they are seen for follow up in the outpatient clinic. We currently have an IRB-approved existing recruitment database through the Ralph H. Johnson VAHCS (IRB# 43107 "VA Stroke Rehabilitation Research Database", [name], PI). This database is initially populated with an existing patient registry kept by Neurology Service which includes approximately 500 post-stroke patients seen at the Ralph H. Johnson VAHCS or one of the 5 affiliated community-based outpatient clinics (CBOC's). Of these, approximately 350 meet the age criteria for enrollment in the proposed study (excluding duplicates from our MUSC registry, see below). Ongoing recruitment is expected to add 5-8 more subjects each month.

The MUSC Stroke Program holds Joint Commission's Certificate of Distinction for Primary Stroke Centers which recognizing centers that make exceptional efforts to foster better outcomes for stroke care. The MUSC Stroke Program alone sees over 50 new stroke patients per month and routinely screens all patients for eligibility to our various research studies. In addition, since the proposed research investigates

stroke recovery, it will have access to resources at the NIH-funded Center of Biomedical Research Excellence (COBRE) in Stroke Recovery at MUSC. [name] is a currently a junior investigator in this center and will be able to access the Clinical and Translation Tools and Resources (CTTR) Core for subject recruitment support. The CTTR Core provides recruitment resources through a bioinformatics-enabled database registry via a separate IRB approved database (IRB# 37803 "RESTORE"). Currently, there are 682 post-stroke subjects (93 veterans), 560 of whom are \leq 75 years old, in our database registry and recruitment is expected to add 3-5 more subjects each week. Thus, with such a large cohort of stroke patients, we should have no difficulty in recruiting the subjects required to address our aims.

The study coordinator will obtain contact information from the recruitment database(s) and will make initial contact via the telephone. If they meet inclusion criteria as capable of being obtained over the phone, potential participants will be requested to come in person to the research laboratories where they will participate additional testing as allowed by the database IRB (Pro00037803 or Pro00043107). The participant will engage in the consent process in a privated area in the research space, and consent may be obtained by the PI, the study coordinator, or a member of the investigative team.

9.0 Consent Process

The consent process will take place in the labs or private office of the study coordinator at the time of the subjects' visit. The PI, Co-PI's, investigators and study coordinator are experienced in consenting subjects. At least one of these study personnel will be onsite to review the consent document with the subject and answer any questions. The subject will be asked to document his or her consent in writing on the informed consent document. The process will occur in privacy in one of several labs listed in the protocol.

The participant will be given the opportunity to discuss the protocol and ask any questions that they may have. After the conversation, the participant will be given the opportunity to consent or not. The PI, the study coordinator, or members of the research team may obtain consent.

10.0 Study Design / Methods

This proposal seeks to develop a theory-based clinical decision-making framework for the training of walking recovery after stroke based on how different biomechanical patterns of walking illustrate distinct motor control deficits. 72 individuals with unresolved propulsion asymmetry after chronic stroke (greater than six months post-stroke, so additional natural recovery is not expected) will be evaluated to determine their baseline level of Pp: low Pp (≤ 0.47) and high Pp (≥ 0.53) (0.47 to 0.53, equal to 3 standard deviations around the mean for healthy controls). Individuals will be randomly assigned to one of three intervention groups (INCLINE, DECLINE, or CONTROL training), and we will recruit into each training group an equal number of 10 individuals with low or high Pp (Figure 6). Each participant in INCLINE training will walk four 5-minute bouts at the highest speed they can tolerate for 5 minutes (up to SSWS and at least 50% of SSWS) on a 10% up-sloped treadmill followed by 6 minutes of level overground walking at the pace that they can maintain (breaks are allowed as necessary while the clock continues to run). INCLINE training will focus on increasing force production and promoting increased and symmetrical hip extension. Those in DECLINE training will also walk with the same number of bouts, intensity, and overground walking as INCLINE on a 10% down-sloped treadmill, limiting hip extension, and promoting effective stance to swing transitions through increased knee flexion and eccentric control of the knee. During the 6-minute walk, each participant will focus on specific gait details targeted in the INCLINE/DECLINE trials (e.g. increased hip extension, increase paretic leg loading, or improved stance to swing transition). CONTROL participants will walk four 5-minute bouts at their SSWS on a flat treadmill followed by 6 minutes of level overground walking at the SSWS, controlling for equal time of walking activity. Placement into the INCLINE, DECLINE, or CONTROL training groups will be randomized based on a computerized randomization by the study statistician. Each individual will complete 12 sessions (three times a week for four weeks). Clinical and biomechanical outcome measures will be collected pre- and post-training and after a one-month follow-up period. In addition, we will collect a battery of clinical outcome measures before and after training. Spatiotemporal variables (including SSWS) will be collected before and after each session. All clinical and biomechanical assessments will be conducted by an evaluator blinded to training group allocation.

[figure not shown]

Figure 6. Study design and flow of assessments and training.

11.0 Data Management

As a clinical trial, the details of this project will be entered into clintrials. Clinical data from assessment sessions will be recorded on hard copies (stored in a locked file cabinet in the Ralph H. Johnson VAHCS rehabilitation research space) and entered into a RedCAP electronic database by the project coordinator immediately after each session. These data will be de-identified for further analysis. Only the PI will have

access to de-identified data. Gait data will be analyzed using a custom MATLAB program, automatically populating a LabView Data Viewer from which customized data may be retrieved. The research coordinator will check the data entry, and pool all data into a group-wide de-identified spreadsheet. All data from training sessions will also be analyzed and stored using an automated MATLAB program. All electronic data will be stored on a secure server that is backed-up nightly. Upon completion of all Aims, the de-identified spreadsheets and group assignment list will be shared with the statistician for analysis. The de-identified dataset will be available for sharing with other investigators, and this trial will be registered in the NIH-supported registry.

Sample Size Determination and Statistical Approach: A total of 72 individuals post-stroke will be recruited for this study. We are assuming an attrition rate of 20% resulting in a final sample size of 60 for statistical analyses, ideally 10 in each combination of baseline group (low and high Pp) and intervention (INCLINE, DECLINE, and CONTROL training). 10% is consistent with attrition rates from previous trials of locomotor rehabilitation conducted by our group,⁴³ but we have chosen a more conservative rate of 20% based on the novelty and intensity of the intervention. There will be two strata of 30 individuals each with baseline low Pp and high Pp, respectively. From those strata, using block randomization, the subjects will be equally randomized into the INCLINE, DECLINE, and CONTROL training (10 in each training cell). The power analysis was based on our pilot training data for INCLINE and DECLINE combined compared to CONTROL. For the power analysis, we used a repeated measures model with an AR(1) correlation value of 0.45 which we obtained from the pilot data. With an average standard deviation of 0.35 (also obtained from the pilot data) and 80% power, with 10 subjects per group we will be able to detect a difference of at least 0.20 between the intervention groups and CONTROL group. A log transformation was applied to achieve normality. Also, we will longitudinally evaluate speed at each session. We will therefore conduct a repeated measures 2-way ANOVA and test the relevant hypotheses using contrasts in a Bonferroni post-hoc analysis. We will include an adjustment for baseline Pp group, intervention group, time, and their interactions. Depending on the within subject correlation across time (which we anticipate to be high) this could also provide additional power. Therefore, in a secondary analysis we will be able to examine several covariates, including the sub-types mentioned above. For each Aim, each variable will be assessed utilizing a repeated measures analysis of variance (baseline Pp, group and time) to evaluate the interaction between baseline Pp, group and time as well as the main effects of treatment for each group and group assignment at each time point. Since pilot data required a log transformation of SSWS, we will assess the final SSWS outcome for normality and perform a transformation if necessary. All power estimates were conducted by a biostatistician ([name]) using PASS 2008 (NCSS, Kaysville, Utah). Spaghetti plots and descriptive statistics regarding HR, BP, and RPE responses to INCLINE and DECLINE training will be reported prior to formal analyses. Patterns of attrition between the 2 groups will also be compared.

[name] will be the unblinded statistician who will track the trial to ensure adverse events are not disproportionately harmful to any one group of participants. After every adverse event, a report will be prepared by [name] and shared with the team and the MUSC IRB. All serious adverse events will be analyzed by the investigative team and the MUSC Institutional Review Board. Serious adverse events are defined as 1) being unexpected; 2) related to a subject's participation in research; and 3) that subjects are at greater risk of harm than was previously recognized. If > than 10% in each cell have a serious adverse event, we will evaluate the circumstances and decide if the event was caused by a particular treatment. If a majority of team or the IRB decides that the adverse event was related to intervention, subsequent randomizations will be stopped.

12.0 Provisions to Monitor the Data to Ensure the Safety of Subjects (if applicable)

Informed consent will be obtained by the on-site R&D IRB approved VA research staff (i.e. research therapist, research assistant, investigator, coordinator, or other associated trained staff) in a private room located at the Center for Rehabilitation Research in Neurological Conditions (CNNRC), Dept. of Health Sciences and Research, MUSC, [name].2nd Floor, Room C214 and 213 (designated VA space through MOU between MUSC and VA).

All hard copies of signed consent forms and associated data (intake form) will be stored in a locked office located on the 2nd floor, Room C213, north wall, in a badge access and secure building at the Medical University of South Carolina ([name], designated VA space through a Memorandum of Understanding between MUSC and VA).

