1.0 Objectives / Specific Aims

Specific Aim 1: Determine the efficacy of motor control deficit guided personalized training on SSWS compared to non-personalized and control interventions. Hypothesis: Individuals receiving walking rehabilitation personalized to their baseline motor control deficit (INCLINE for low Pp and DECLINE for high Pp) will exhibit significantly improved SSWS compared to those receiving non-personalized and control interventions.

Specific Aim 2: Determine the efficacy of motor control deficit guided personalized training on increasing symmetry of Pp compared to non-personalized and control interventions. Hypothesis: Individuals receiving walking rehabilitation personalized to their baseline motor control deficit will exhibit significantly improved symmetry of Pp compared to those receiving non-personalized and control interventions.

Specific Aim 3: Determine if the personalized intervention increase the positive response rate compared to non-personalized and control interventions, and to further advance personalized interventions by identifying factors that predict response. Hypothesis 3.1: A higher percentage of individuals receiving personalized interventions will “respond” than those receiving non-personalized and control interventions. Hypothesis 3.2: Discreet sets of clinical and biomechanical variables will predict responses in those with differing baseline motor control deficits.

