Treatment Determined by Baseline Motor Control Deficit: Our pilot data reveal that the two patterns are most effectively rehabilitated by different treatment strategies: 1) low Pp by walking on an inclined treadmill requiring increased force production and promoting increased and symmetrical hip extension^{24,25}; and 2) high Pp by walking on a declined treadmill, limiting hip extension and promoting effective stance to swing transitions, increasing knee flexion, and encouraging improved knee extensor eccentric control.^{24,25}

Manipulation of Task Mechanics to Meet Specific Training Goals: Successful uphill walking requires increased force production bilaterally in order to maintain forward progression. Specifically,

spatiotemporal symmetry and paretic hip extension are increased following incline walking post-stroke when the incline is at least eight degrees.²⁶ Ground reaction forces and joint moments increase with concomitant increases in slope, particularly in the anterior-posterior direction representative of propulsion,²⁷ and incline walking is associated with increased knee extensor and ankle plantarflexion activity producing the additional propulsion required to step uphill.²⁸ Gama et al. recently trained individuals post-stroke with body-weight support (BWS) and a 10% incline and compared to a group undergoing level treadmill training with BWS.²⁹ Incline-trained individuals demonstrated significant improvements over the control group in walking speed ($p=0.002$) and paretic step length ($p=0.02$). However, all individuals trained at the same direction of treadmill inclination.²⁹

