low-pass filtered with a fourth-order, zero-lag digital Butterworth filter. To optimize capture of steady state data on the treadmill, subjects will walk for approximately 10 seconds to achieve steady state prior to the 30 seconds of data collection (40 seconds per trial). Two trials will be collected at the treadmill self-selected speed and two trials at the fastest comfortable speed. Biomechanical data collections will allow for secondary analyses of associated kinematic and kinetic variables (e.g. force impulse, COMa by gait cycle phase, joint moments/power/work, and joint angles). At baseline testing, post-testing, and at the beginning of *each session*, participants will walk on a 16 ft. long gait mat (GAITRite) to measure SSWS and fastest comfortable walking speed (FCWS) and other spatiotemporal parameters. Subjects will be permitted a practice trial, and then be asked to complete two trials at each speed. A safety harness mounted to the ceiling will protect the subject but will only support their body weight in the case of a loss of balance. Trained study personnel will be present for all testing sessions as needed.

Clinical Assessments: The proposed assessments are standard to most post-stroke intervention trials. As the primary aim of this proposal is to improve functional outcomes using an intervention that is clinically translatable, it is imperative to include assessments routine to clinical rehabilitation. The below measures reflect a battery of body structure and function, activity, and participation measurement to reflect a broad range of clinical assessment across the rehabilitation model (ICF) as has been previously advocated.⁵⁰ All clinical assessments will be conducted by a physical therapist evaluator blinded to group allocation (different than the training physical therapist) within the Center for Rehabilitation Research in Neurological Conditions.

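### 72 recruited with 20% attrition leaves 57.6 analysable, not 60, and the only stated power is for pooled slope training versus CONTROL, so none is stated for the Aim 1 contrasts

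*Combined protocol and SAP*

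**What the plan says.** **Numbers.** Sections 6.0 and 11.0 carry the same text: 72 recruited, 20% attrition, 60 left for analysis, ideally 10 in each of the six combinations of baseline Pp group and training. They then describe two strata of 30, randomized equally with 10 in each training cell. Section 10.0 also speaks of recruiting 10 low-Pp and 10 high-Pp participants into each training.

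**Power.** Only Section 11.0 gives a power statement: "The power analysis was based on our pilot training data for INCLINE and DECLINE combined compared to CONTROL". It uses SD 0.35, AR(1) correlation 0.45 and 80% power, and concludes that "with 10 subjects per group we will be able to detect a difference of at least 0.20 between the intervention groups and CONTROL group". The next sentence is "A log transformation was applied to achieve normality", and a later one says that pilot SSWS needed a log transformation. Alpha, sidedness and the number of repeated measures are not given. The planned analysis is a repeated-measures ANOVA with baseline Pp, training, time and their interactions, tested by Bonferroni contrasts.

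**Aim 1.** Section 1.0 compares personalized training (INCLINE for low Pp, DECLINE for high Pp) with non-personalized and control training on SSWS. Section 2.0 adds: "Our pilot data reveal that the two patterns are most effectively rehabilitated by different treatment strategies".

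**Timing of SSWS.** Section 4.0 measures walking speed at baseline, at post-testing and at the start of each session. Section 10.0 says "Spatiotemporal variables (including SSWS) will be collected before and after each session", and also "Clinical and biomechanical outcome measures will be collected pre- and post-training and after a one-month follow-up period".

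**The concern.** Two things do not line up. The analysable sample of 60 is the figure on which the cell sizes rest, and the plan's own recruitment and attrition inputs do not produce it.

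Second, both Pp strata are randomized equally to all three trainings, so INCLINE and DECLINE combined is half matched and half mismatched to the deficit. The trial's central question is whether matching beats mismatching, and the plan expects the halves to differ. The 80% is attached to another comparison. A reader could carry it over to Aim 1 without knowing whether that is justified, and a null personalized versus non-personalized result would be hard to interpret without a stated detectable difference.

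**Working it through.** **Attrition.** Inputs from Sections 6.0 and 11.0.
- 72 x 0.80 = 57.6; 57.6 / 6 = 9.6 per cell; two cells make 19.2 per Aim 1 group.
- 1 - 60/72 = 16.7% attrition.
- 60 / 0.80 = 75 would have to be recruited. The figure 72 equals 60 x 1.2, which may be how it arose.

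**Reproducing the stated power.** Inputs from Section 11.0: SD 0.35, AR(1) 0.45, difference 0.20. Assumed: two-sided alpha of 0.05, or 0.025 as a two-contrast Bonferroni; M measures averaged over time; normal approximation.

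Variance factor: v = (1/M)[1 + 2 Σ (1 - k/M) 0.45^k], k = 1 to M-1. 
SE = 0.35 x √(v(1/n1 + 1/n2)). Power = Φ(0.20/SE - z). Detectable difference at 80% = (z + 0.842) x SE.

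- 10 v 10, M = 12 (one per session), alpha 0.05: v = 0.199, SE = 0.0698, power 81.7%.
- 10 v 10, M = 14 (Section 4.0: 1 + 1 + 12), alpha 0.025: v = 0.173, SE = 0.0651, power 79.7%.
- 10 v 10, M = 3 (assessment visits), alpha 0.05: v = 0.578, power 39.0%.
- 10 v 10, M = 27 (Section 10.0 at most: 2 x 12 + 3), alpha 0.05: power 98.7%.
- 40 v 20 (10 read as the cell size, slopes pooled), M = 3, alpha 0.05: power 78.3%.

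With 10 per group as written, the claim reproduces at 12 to 14 measures. It does not reproduce on the three visits unless 10 is read as a cell size.

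**Same inputs at 19 v 19, the size of an Aim 1 contrast.**

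| Summary of SSWS | v | Detectable at 80% (alpha 0.05 / 0.025) | Power for 0.20 (alpha 0.05 / 0.025) |
|---|---|---|---|
| Mean of 14 | 0.173 | 0.13 / 0.15 | 98.9% / 97.7% |
| Mean of 12 | 0.199 | 0.14 / 0.16 | 97.7% / 95.6% |
| Mean of 3 visits | 0.578 | 0.24 / 0.27 | 63.9% / 53.0% |
| Mean of post and follow-up | 0.725 | 0.27 / 0.30 | 54.3% / 43.1% |
| Pre-post change, v = 2(1 - 0.45) | 1.10 | 0.33 / 0.37 | 39.0% / 28.7% |

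The last three rows take 0.45 as the correlation between adjacent visits, which the plan does not say. The means of 3, 12 and 14 include pre-training values, so they are optimistic guides to a treatment effect.

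**Effect of the slip on power** (alpha 0.05): 10 v 10 to 9.6 v 9.6 at M = 12, 81.7% to 80.1%; 20 v 20 to 19.2 v 19.2 at M = 3, 66.1% to 64.4%.

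**Scale.** On the natural log (base assumed), 0.20 is a ratio of e^0.20 = 1.221. Over the 0.2 to 1.0 m/s entry range that is 0.2 x 0.221 = 0.04 to 1.0 x 0.221 = 0.22 m/s.

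**The case against.** The 0.20 is a detectable difference, fixed by SD, correlation, sample size, number of measures and alpha. Under the same model it transfers to any contrast of equal or larger size, and an Aim 1 contrast has about 19 per group rather than 10. Moreover, 10 per group can be read as the cell size; a single-cell comparison within low Pp, such as INCLINE versus CONTROL or INCLINE versus DECLINE, would itself be an Aim 1 question. The planned model and contrasts can test Aim 1. The log scale is well supported, and the word ideally next to 10 per combination suggests completer targets. The Preliminary Studies, which the text cites, are not in the documents and may hold more.

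Most of this stands. A reader might infer that the pooled calculation has no bearing on Aim 1, or that Aim 1 is underpowered. The documents support neither: with 10 per group and 12 to 14 measures, power for 0.20 at 19 v 19 is about 98%. The 64% figure needs three visits, which match the claim only as 40 v 20.

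What does not fall away is that the sentence naming the powered comparison pools the slopes, and that no detectable difference or expected effect is stated for either Aim 1 contrast. The transfer also needs the number of measures and alpha, which are not given. The attrition arithmetic is not rebutted. Completer targets are a plausible reading of 30 and 10, but the text goes on to randomize 10 per cell, and they would not turn 57.6 into 60.

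**Conclusion.** Both points hold and both are matters of restatement. The analysable number is 57.6, not 60, under the plan's own inputs; this is certain and small, at most about 2 power points. The stated 80% belongs to pooled slope training versus CONTROL, so power for personalized versus non-personalized and for personalized versus CONTROL is unstated. It is not shown to be low: about 98% for a difference of 0.20 at 19 v 19 if the 10-per-group, 12-to-14-measure reading applies, and 29% to 64% across the assessment-visit summaries and the two alphas tried. These figures assume the pilot SD and AR(1) value carry over, two-sided alpha of 0.05 or 0.025, and a normal approximation. They illustrate the spread and are not replacement values. The documents give no expected size for the matched versus mismatched difference, so whether 0.20 is realistic for that contrast cannot be judged.

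**What to change.** 1. In Sections 6.0 and 11.0, restate the analysable number as about 57 (9 to 10 per cell), or the assumed attrition as 16.7%.
2. Say that 30 per stratum and 10 per cell are completer targets, if that is meant, and align Section 10.0. With all 72 randomized equally, the randomized numbers would be 72/2 = 36 and 72/6 = 12.
3. In Section 11.0, rerun the calculation and give the detectable difference at 80% power for personalized versus non-personalized and for personalized versus CONTROL, at about 19 v 19, under the planned repeated-measures model and the Bonferroni alpha.
4. With it, state alpha and sidedness, what group means, the number and timing of SSWS measures (reconciling Sections 4.0 and 10.0), and that 0.20 and 0.35 are on the log scale, if so.

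The cost is wording and one rerun of the power calculation, with no extra patients. The downside is that the stated figures may become slightly less favourable.

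### Bonferroni is valid but needlessly conservative for the two comparisons named in Hypotheses 1 and 2; Holm holds the same family-wise error and never has less power

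*Combined protocol and SAP*

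**What the plan says.** Section 1.0 of the combined protocol and SAP fixes the comparisons in advance. Hypothesis 1 concerns people given training matched to their deficit, defined as "INCLINE for low Pp and DECLINE for high Pp". The prediction is that they "will exhibit significantly improved SSWS compared to those receiving non-personalized and control interventions". Hypothesis 2 uses the same form for propulsion: they "will exhibit significantly improved symmetry of Pp compared to those receiving non-personalized and control interventions". Read plainly, each hypothesis has a stated direction and two comparators.

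Section 11.0, under the sample size and statistical approach, plans a repeated-measures ANOVA and will "test the relevant hypotheses using contrasts in a Bonferroni post-hoc analysis". Later in the same paragraph, each variable for each Aim is analysed "to evaluate the interaction between baseline Pp, group and time", along with main effects.

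The documents do not list the contrasts, say how many the correction covers, give alpha or sidedness, or say whether one significant comparison or both would support an Aim. The only power statement is for INCLINE and DECLINE combined against CONTROL. It takes an SD of 0.35, 80% power and groups of 10, and its conclusion is "we will be able to detect a difference of at least 0.20 between the intervention groups and CONTROL group". No multiplicity correction is mentioned there.

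**The concern.** Bonferroni tests every contrast at the reduced level, whatever the other contrasts show. Holm tests the smaller p-value at that reduced level and, if it is significant, tests the next at a less strict level. With two contrasts, the second is tested at the full 5%. Family-wise error stays at or below 5% under both, and Holm rejects everything that Bonferroni rejects and sometimes more. Using Bonferroni for prespecified comparisons therefore gives up power without improving the error guarantee.

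This matters because the trial is small. With 10 completers in each of the six cells, each side of a personalized contrast has 20 people. The power statement concerns a different contrast, so the plan documents no reserve of power for these comparisons.

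**Working it through.** **The plan's own figure.** Inputs from section 11.0: difference 0.20, SD 0.35, AR(1) correlation 0.45, 80% power, 10 per group. The number of repeated measures m and alpha are not given. The variance of a mean of m AR(1) measures is SD² × VF, with VF = (1/m)[1 + 2Σ(1 − k/m)0.45^k], k = 1 to m − 1. Power = Φ(0.20 / (0.35√(VF(1/n₁ + 1/n₂))) − 1.960) at two-sided 5%.

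| Groups | m | VF | Power |
|---|---|---|---|
| 10 v 10 | 1 | 1.000 | 24.8% |
| 10 v 10 | 3 | 0.578 | 39.0% |
| 10 v 10 | 12 | 0.199 | 81.7% |
| 20 CONTROL v 40 combined | 3 | 0.578 | 78.3% |
| 20 v 20 | 3 | 0.578 | 66.1% |

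About 80% is attainable under some choices of m and grouping, so the figure is not disputed. It does not give the power of either personalized contrast. The last row shows what one of them would have with three measures and the same difference.

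**Assumptions for the comparison of procedures.** Two contrasts; two-sided 5% overall; 80% power for each before correction. None of these is stated in the plan for these contrasts. The correlation follows from the design: with equal groups of 20 and a shared personalized group, the covariance is σ²/20 and each variance is 2σ²/20, so the correlation is 0.5.

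**Set-up.** The mean of each test statistic is 1.960 + 0.842 = 2.802. Critical values are 1.960 at 5% and 2.241 at 2.5%. J(c₁, c₂) is the bivariate normal probability that the two statistics exceed c₁ and c₂.

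- One contrast, Bonferroni: Φ(2.802 − 2.241) = 0.7123.
- Both significant, Bonferroni: J(2.241, 2.241) = 0.5721.
- One at 5% and the other at 2.5%: J(1.960, 2.241) = 0.6244.
- Both significant, Holm (both pass 5%, at least one passes 2.5%): 2 × 0.6244 − 0.5721 = 0.6767.
- One contrast, Holm (it passes 2.5%, or passes 5% while the other passes 2.5%): 0.7123 + (0.6244 − 0.5721) = 0.7646.
- Both significant with each tested at 5%: J(1.960, 1.960) = 0.6872.
- At least one significant, the same under Bonferroni and Holm: 2 × 0.7123 − 0.5721 = 0.8525.

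**Sensitivity to per-contrast power** (correlation 0.5, chance that both are significant):

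| Power before correction | Bonferroni | Holm | Gain, points |
|---|---|---|---|
| 40% | 15.4% | 22.6% | 7.2 |
| 60% | 32.2% | 42.5% | 10.3 |
| 70% | 43.5% | 54.4% | 10.9 |
| 80% | 57.2% | 67.7% | 10.5 |
| 90% | 74.5% | 82.6% | 8.1 |
| 95% | 85.4% | 90.9% | 5.5 |

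At 80% power, varying the correlation from 0 to 0.9 moves the gain from 12.5 to 7.7 points.

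**Error rates** (simulation, correlation 0.5). With both nulls true, the chance of any false win is 4.7% under Bonferroni and the same under Holm, whose first step is identical; without correction it is 9.1%. With one null true and the other contrast at 80% power, the false-win rate is 2.5% under Bonferroni and 4.1% under Holm. Both are below 5%.

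**The case against.** Bonferroni is valid and conservative, so preferring Holm is a matter of efficiency. That stands, and it is why this is a recommended improvement and not a correction of an error.

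The illustrated gain is not a figure for this trial. The number of contrasts, the alpha and the 80% are assumptions, and the plan's 80% belongs to another contrast. That also stands, so the range matters more than any single value. The gain of about 10 points is in the chance of winning both; for one contrast it is 76.5 − 71.2 = 5.3 points. The Bonferroni family may also exceed two, because the plan lists main effects and comparisons at each time point as well.

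A reader might infer three stronger claims that the documents do not support.

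- **That the contrasts can be tested only after a significant omnibus test.** Section 11.0 places the ANOVA and the contrasts side by side and makes neither depend on the other. The hypotheses are fixed in section 1.0, so the label post hoc can simply mean follow-up contrasts.
- **That an Aim succeeds only if both comparators are beaten.** This rests on the word joining the two comparators. No success rule is written, and a pooled comparator is also a possible reading.
- **That Bonferroni brings no error-rate benefit over testing each contrast at 5%.** For a claim that needs both wins, it brings none that is needed. If either win could be reported alone, Bonferroni holds the chance of any false win at 4.7%, against 9.1% uncorrected.

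**Conclusion.** The point holds as an efficiency improvement. Whatever the size of the family, Holm matches Bonferroni's family-wise control and is never less powerful; that conclusion needs none of the illustrative assumptions. Its size does. With two contrasts, two-sided 5%, 80% power each and correlation 0.5, single-contrast power rises by 5.3 points and the chance of winning both by 10.5 points. For per-contrast power of 40% to 95%, the latter gain is about 5 to 11 points.

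A rule that both comparators must be beaten is not simply better. It allows each contrast to be tested at 5% for the joint claim and gives a 68.7% chance of supporting the Aim, but it gives up single-win claims, for which the chance of at least one is about 85.3% under Bonferroni or Holm.

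**What to change.** For Aims 1 and 2, name two contrasts as the planned tests: personalized against non-personalized, and personalized against CONTROL. Replace Bonferroni with Holm across these two at an overall two-sided 5%, and report ordinary 95% intervals beside the adjusted p-values.

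If the sponsor intends an Aim to be supported only when both comparators are beaten, say so instead. Each contrast may then be tested at two-sided 5%, with both required in the favourable direction and no claim made from one alone. That choice is the sponsor's and should be made before the data are seen.

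The cost is one or two sentences of analysis text, with no added participants, visits or data. The small downside of Holm is that it has no simple simultaneous confidence intervals, so an ordinary interval may exclude zero where the adjusted p-value is not significant.
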